### **Statistical methods for the internal pilot study**

The first 20 patients will be enrolled and randomly assigned into placebo and oxytocin group. The primary outcome ARI will be measured at the baseline and last visit for each patient. The change of ARI will be calculated as the measure at the last visit minus the measure at the baseline for each patient. The treatment status of each patient will be labeled as A and B by the third party, and all persons associated with the internal pilot study will be kept blinded for group assignment. The SD of the change of ARI will be estimated for each intervention group, and will be used to compute the pooled SD for the internal pilot study. Recalculation of the sample size will be performed using a two sample independent t-test and the pooled SD. The retention rate will be assessed as well.

The data on genetic polymorphisms and OT-treatment outcomes on the neural and psychological measures will be used primarily as pilot data to advise future larger-scale studies. OXTR SNPs vary in frequency in western populations, but there should be sufficient exemplars of varying genotypes to allow preliminary analyses. For example, a commonly-identified OXTR SNP associated with variation in social behavior (rs53576) occurs in frequencies of 53.5% and 46.5% for the risky genotype (A/A and A/G) relative to resilient genotype (G/G) in a Caucasian sample (Jacob et al., 2007).

Finally, we will simultaneously test all measures (e.g., at baseline) in a multivariate analysis to determine the most important measures for predicting outcome in terms of behavioral change (Ecker et al., 2010). It is hoped that this will show which ones of the variables are the best predictors of treatment response, and which aspects are best influenced by treatment.

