## **CHARACTERISTICS OF THE SUBJECT POPULATION**

### **4. Accrual**

**Is this study conducted solely at sites under the oversight of the Joint Pediatric IRB (e.g. UNMC, TNMC, CH&MC, UNO)?**

Yes

**A. What is the total number of subjects (per group, as applicable) needed to complete the research in order to achieve the scientific objectives of the research?**

104 subjects are needed to complete the trial (52 per treatment group).

**B. What is the statistical or other justification for the total number of subjects needed to complete the research in order to achieve the scientific objectives of the research?**

The primary outcome is the change of Affective Reactivity Index (ARI) from the baseline to the last visit. A sample size of n=52 per group will provide 80% power to detect a difference between the group means of -4.0 in the change of ARI of -4.0 at the significance level of

0.05 using a two-sided two-sample t-test, assuming the mean of -4.0 and the standard deviation of 7.2 in the oxytocin group, and the mean of 0 and the standard deviation of 7.2 in the placebo group.

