#### **Sample size for the internal pilot study**

Given the uncertainty regarding the parameter used to calculate the sample size, an internal pilot study will be conducted to obtain reliable estimate of standard deviation (SD) to recalculate the sample size and assess the retention rate. The minimum size for the internal pilot study,  $n=10$  per group (19% of the pre-planned sample size) will be considered.

---

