#### **C. Based on the anticipated number of screen failures and/or subject withdrawals, what is the maximum number of subjects that will need to be consented in order to achieve the scientific objectives of the research?**

A maximum of 140 subjects will be consented

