#### **17. Risk Classification**

##### **What is the overall risk classification of the research?**

Minimal risk

◆ Greater than minimal risk

Significant risk

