**Withdrawal Criteria**

1. Initiation of any medication that may have psychotropic effects (newly introduced antidepressants, antipsychotics, anxiolytics, stimulants, and non-stimulant ADHD medications).

2. Discovery of neurologic disorder (including seizures) or anatomical abnormality of brain (including brain neoplasm, hydrocephalus) during participation.
3. Discovery of substance abuse or dependence.
4. Inability of the participant to complete fMRI or MEG due to claustrophobia despite previous questioning.
5. Participants who do not want to continue with the study.
6. Participants who cannot or will not cooperate with study procedures.
7. Participants who experience strong discomfort or develop side effect following the administration of oxytocin or placebo nasal spray.
8. Participants who experience significant worsening of psychiatric symptoms that warrant change of treatment (such as inpatient psychiatric hospitalization).

**G. Describe the specific criteria for halting or early termination of the study (for example statistical evidence of unacceptable toxicity or early demonstration of efficacy or lack of efficacy).**

The study would be halted in followings;

1. Early evidence showing lack of efficacy on irritability or worsening of irritability by oxytocin treatment: After the preliminary phase of the study (10 patients on each arms of oxytocin and placebo trial), if it turns out that children and adolescents experience significant worsening of their psychiatric/behavioral symptoms, or have no change in their psychiatric/behavioral symptoms, we then will consider terminating the study.
2. MEG and/or fMRI become inoperable
3. Serious injury related to procedure (MEG, fMRI, or oxytocin administration) occurs

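### Does the internal-pilot recalculation need a stated minimum and maximum sample size before it can be trusted?

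*Combined protocol and SAP*

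**What the plan says.** Section 4.A: "104 subjects are needed to complete the trial (52 per treatment group"). Section 4.B gives the basis. The primary outcome is the change in ARI from baseline to the last visit, and "A sample size of n=52 per group will provide 80% power" for a difference of -4.0, with an SD of 7.2 in each arm and a two-sided two-sample t-test at 0.05.

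The next paragraph of 4.B introduces the internal pilot: "Given the uncertainty regarding the parameter used to calculate the sample size", a pilot of 10 per group will supply an estimate of the SD, from which n is recalculated, and a look at retention. The only minimum named there is the size of the pilot itself.

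Section 12.F gives the rule: "Recalculation of the sample size will be performed using a two sample independent t-test and the pooled SD". It adds: "The retention rate will be assessed as well". Arms are labelled A and B by a third party, and those involved in the pilot stay blinded.

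Section 4.C sets the recruitment limit, framed around screen failures and withdrawals: "A maximum of 140 subjects will be consented".

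Two other places bear on the point. Section 17 classes the research as "Greater than minimal risk". Section 18.G allows termination to be considered at the same milestone: "After the preliminary phase of the study (10 patients on each arms of oxytocin and placebo trial").

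**The concern.** A pooled SD from 10 per arm has 18 degrees of freedom and is imprecise. If n follows it in both directions, a low estimate that arises by chance shrinks the trial even when the planning SD was right. A high estimate can call for more completers than 140 consents can supply, which is at most 70 per arm even if nobody fails screening or withdraws. Neither 4.B nor 12.F says which moves are allowed, and 12.F does not restate the -4.0 difference or the 80% target.

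At stake would be the power of the primary comparison. The plan quotes 80%, but the trial as run would have a random sample size. If the rule were settled only after the pilot data were in, the choice could also look driven by the data.

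**Working it through.** **Inputs.** Difference 4.0, SD 7.2, two-sided 0.05, 80% power and 52 per arm (4.A, 4.B); pilot of 10 per arm (4.B); pooled SD and t-test recalculation (12.F); 140 consents (4.C). Assumptions: the recalculation keeps 4.0, 80% and 0.05; the final analysis is the ordinary t-test on all patients; SDs of 6, 8 and 9 are illustrative.

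**Step 1: reproduce the plan's figure.** Noncentrality = (4.0/7.2) × √(52/2) = 0.5556 × 5.099 = 2.833, with 102 df. Noncentral-t power is 80.1% at 52 per arm and 79.3% at 51. The solution for 80% is n = 51.84, so 52. The stated 80% is right.

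**Step 2: distribution of the recalculated n at true SD 7.2.** The pilot SD s satisfies 18 s²/7.2² ~ χ² with 18 df.

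- n is below 52 when s ≤ 7.14: 18 × (7.14/7.2)² = 17.70, probability 0.525.
- n is 40 or less when s ≤ 6.306: 18 × (6.306/7.2)² = 13.81, probability 0.258.
- n is above 70 when s > 8.388: 18 × (8.388/7.2)² = 24.43, probability 0.141.
- The median n is about 50, and the central 95% range is about 25 to 91 per arm.

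**Step 3: power of the two-stage design.** Simulation with 1,000,000 trials per cell: pilot SD drawn, n recalculated by the t-test formula, pilot and later data pooled.

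| True SD | Fixed 52 | No floor, no ceiling | No floor, at most 70 | Floor 52, no ceiling | Floor 52, at most 70 |
|---|---|---|---|---|---|
| 6 | 92.0% | 79.0% | 79.0% | 92.4% | 92.4% |
| 7.2 | 80.1% | 78.3% | 77.7% | 84.1% | 83.6% |
| 8 | 71.4% | 77.9% | 75.6% | 80.7% | 78.3% |
| 9 | 61.2% | 77.7% | 70.6% | 78.6% | 71.4% |

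If n may fall but never exceed 52, power at SD 7.2 is 74.3%. The range at the planning SD is therefore about 74% to 84%. Against the fixed design, the two-way rule without limits loses 80.1 - 78.3 = 1.8 points at SD 7.2 and gains 77.7 - 61.2 = 16.5 points at SD 9.

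**Step 4: type I error, no ceiling.** Without a floor: 5.4%, 5.3% and 5.2% at SD 6, 7.2 and 9. With a floor of 52: 5.0%, 5.1% and 5.1%.

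**Step 5: what a floor of 52 costs.** Mean n per arm, no ceiling, rule against floor: SD 6, 36.8 and 52.8 (16.0 more); SD 7.2, 52.4 and 58.9 (6.5 more); SD 8, 64.3 and 67.4 (3.1 more); SD 9, 81.0 and 82.0 (1.0 more).

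**Step 6: the consent limit.** Sections 4.A and 4.C together imply a planning yield of 104/140 = 74%. At that yield 140 consents give 140 × 0.743 = 104 completers, 52 per arm. A floor of 52 and a ceiling of 52 leave n fixed at 52, with 80.1% power at SD 7.2, 71.4% at SD 8 and 61.2% at SD 9. The pilot could then no longer change n at all.

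**The case for a change.** The strongest case for a change is the spread, not the average. When the planning SD is exactly right, about one trial in four would be cut to 40 per arm or fewer, and a fixed 40 per arm has 69% power at SD 7.2. At SD 9 the recalculated n exceeds 70 per arm in 62% of trials, more than 140 consents can supply under any retention. Two or three sentences would settle both matters, and they are best written before the pilot data are seen.

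The omissions are real and the arithmetic stands. Three things limit the force of the argument.

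- The 69% is conditional on a low SD draw. Averaged over all draws, the same rule gives 78.3%.
- The silence is narrower than it looks. The pilot paragraph directly follows the 4.B calculation and names only the SD as the quantity to be re-estimated, so the difference, power and significance level naturally carry over. Section 4.C does give an upper limit; what is missing is a cross-reference.
- The proposed floor does not clearly improve the plan. Letting n fall when the SD is small is a legitimate use of re-estimation, particularly in minors and in research of this risk class. Where the SD is high the floor barely helps (71.4% against 70.6% at SD 9, ceiling 70), and at the implied 74% yield it turns the design back into a fixed one. Protection against a high SD would need a decision on the 140 limit itself, which a floor does not address.

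**Conclusion.** No change follows. The 80% in Section 4.B belongs to a fixed 52 per arm and reproduces at 80.1%. Setting 78% against it compares two different designs, and holds only on the reading that n may fall below 52, which the plan neither permits nor forbids.

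What remains is unwritten detail. Followed literally and without limits, the recalculation does the job 4.B gives it: power of about 78% to 79% across SDs 6 to 9, with type I error of at most about 5.4%. The unstated floor and ceiling move power at SD 7.2 within about 74% to 84%. The low end arises only if n may fall and the consent limit also stops it rising above 52, as it would at the implied 74% yield. Whether to hold n at 52 or let it fall is a choice between extra power and fewer children exposed, and either choice is defensible.

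These figures assume that 4.0, 80% and two-sided 0.05 are kept, that the two arms share a common SD, and that any choice about n rests on the pooled SD alone. They leave out the option in Section 18.G to stop after 10 per arm, which is too loosely defined to compute and could only lower power.

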## **PURPOSE OF THE STUDY AND BACKGROUND**

### **2. Purpose of the Study**

#### **What are the specific scientific objectives of the research?**

The primary objective of this research is to determine the impact of oxytocin on irritability and emotional dysregulation in children and adolescents with DSM-V disruptive mood and behavior disorders. It will also examine the impact of oxytocin on the neural response in the amygdala as well as fronto-amygdala connectivity dysfunction related to irritability and emotional dysregulation in children and adolescents, using fMRI and MEG. Changes in symptom profiles as a result of oxytocin treatment will be assessed for correlation with neural level changes. Differences in the magnitude of treatment responses to oxytocin as a function of polymorphisms in the oxytocin receptor (OTR) will also be assessed.

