**9. Inclusion Criteria**

**What are the specific inclusion criteria?**

**Children/adolescents with disruptive behavior and mood disorders (ADHD, ODD, CD, DMDD)**

1. 10-18 years of age
2. A current diagnosis of ADHD, ODD, CD, or DMDD as determined by the Kiddie-SADS, lifetime version
3. Clinically significant level of irritability as defined by a score of  $\geq 4$  on the Affective Reactivity Index (ARI) (Stringaris et al., 2012)
4. If currently on medication, medication treatment must be stable for at least 6 weeks

with a stimulant medication, alpha 2 agonist, atomoxetine, antipsychotics, mood stabilizers or antidepressant.

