**Symptom Profile Assessment:**

The Affective Reactivity Index (ARI) will be completed at the initial research assessment session and the final research assessment session. ARI is a 7 item inventory (self-report

and parent-report versions) specifically designed to measure irritability and emotional dysregulation (Stringaris et al., 2012). This will be used to measure the outcome of improvement in irritability by oxytocin treatment.

The Behavior Assessment System for Children, second version (BASC-3) will be completed at the initial research assessment session and the final research assessment session. BASC-3 is parent-reported, well-established scale for externalizing/internalizing problem of children and adolescents (Reynolds, 2015). This will be used to measure the outcome of improvement in emotional dysregulation and other related symptoms (externalizing behavior) by oxytocin treatment.

The Inventory of Callous Unemotional trait (ICU) will be completed at the initial research assessment session and the final research assessment session. ICU is a 24 item inventory specifically designed to measure callous-unemotional trait in children and adolescents (Berg et al., 2013; Frick, 2004). This will be used to measure outcome of improvement in callous-unemotional trait by oxytocin treatment. This will be also used to assess covariate function of callous-unemotional trait on treatment response.

The Reactive-Proactive Aggression Questionnaire (RPAQ) will be completed at the initial research assessment session and the final research assessment session. RPAQ is a 23 item inventory (self-report) specifically designed to measure two different types of aggressive behavior, i.e., reactive and proactive aggression (Raine et al., 2006). This will be used to measure outcome of improvement in related symptom of aggressive behavior by oxytocin treatment.

The Clinical Global Impression: Severity and Clinical Global Impression: Improvement scales (CGI-S and CGI-I) will be used at study entry and study completion to quantify, based on clinician's global assessment of the individual, the severity of symptoms compared (study entry and completion) and the degree of improvement (study completion) which may or not be attributable to the study intervention. Other symptom profile measurements will be used to assist the clinician in the rating of this measure.

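### The exploratory analysis of predictors of treatment response specifies no treatment-by-measure interaction, so it is likely to pick up prognosis and regression to the mean rather than response to oxytocin

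*Combined protocol and SAP*

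**What the plan says.** The predictor analysis closes item 12.F, under the subheading on the internal pilot study. The plan reads "we will simultaneously test all measures (e.g., at baseline) in a multivariate analysis to determine the most important measures", with the aim of "predicting outcome in terms of behavioral change". The hope is that this will show "which ones of the variables are the best predictors of treatment response"; the same sentence adds that it should also show what treatment influences most. The type of model is not named. Nor does the text say whether the arms are pooled, analysed separately or limited to oxytocin, or whether treatment enters the model.

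For the primary measure, the same section states: "The change of ARI will be calculated as the measure at the last visit minus the measure at the baseline for each patient". Baseline ARI is available as a candidate predictor, because "The Affective Reactivity Index (ARI) will be completed at the initial research assessment session and the final research assessment session". Entry is also selected on it: "Clinically significant level of irritability as defined by a score of" at least 4 on the ARI.

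The rest of 12.F lists two-sample t-tests, an ANCOVA of BOLD change on treatment group and symptom change, and comparisons of responders with non-responders, where response is 0.4 SD of improvement regardless of arm. None of these names an interaction. Two other places state aims about who responds. Item 2 (Purpose of the Study) will assess "Differences in the magnitude of treatment responses to oxytocin as a function of polymorphisms in the oxytocin receptor". The symptom-profile section will examine how callous-unemotional trait acts as a covariate of treatment response.

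**The concern.** In a placebo-controlled parallel-group trial, a child's change contains regression to the mean, natural course and placebo response as well as any drug effect. A measure that predicts change is prognostic. It predicts response to oxytocin only if its relation to outcome differs between the oxytocin and placebo arms, and that is the one term the plan does not specify.

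For baseline ARI the problem is built in. Baseline enters the outcome with a negative sign, so children who start high tend to show larger falls whatever they receive. At stake is the interpretation of an exploratory result: a severity effect that is equally present on placebo could be reported as a marker of who benefits from oxytocin.

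**Working it through.** **Inputs from the documents.** 104 completers, 52 per arm; expected change in ARI -4.0 on oxytocin and 0 on placebo; SD of change 7.2 in each arm; two-sided 5% t-test (item 4, Accrual). Change is last visit minus baseline (12.F). Entry needs ARI of at least 4 (item 9).

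**Assumptions.** The baseline-to-final correlation, rho, is not in the documents; 0.3 to 0.9 was used. Baseline and final variances are taken as equal. The entry criterion is mimicked by truncating baseline at its mean, because the documents do not show where a score of 4 falls in the distribution; rho then refers to the unselected population. Competing predictors are represented by five further baseline measures, each correlated 0.4 with baseline ARI.

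**The plan's own figure.** The standardised effect is 4.0/7.2 = 0.556. The noncentral t calculation gives 51.84, so 52 per arm, with power 80.1%. The stated sample size reproduces. The predictor analysis has no figure of its own.

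**Correlation of change with baseline under a null drug.** With common variance s²:

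- covariance of baseline and (final - baseline) = rho·s² - s² = -(1 - rho)·s²
- SD of change = s·√(2(1 - rho))
- correlation = -(1 - rho)/√(2(1 - rho)) = -√((1 - rho)/2)

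**Simulation under a null drug.** N = 104, 52 per arm, identical distributions in both arms, 2,000 to 3,000 replicates per scenario. Cells give the percentage of trials in which baseline ARI was significant at 5% as a predictor of change, with no interaction in the model.

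| rho | corr(baseline, change) | Pooled, baseline only | Pooled, truncated | Pooled, five more measures | Pooled, truncated and five more | Oxytocin arm, baseline only | Oxytocin arm, truncated and five more |
|---|---|---|---|---|---|---|---|
| 0.3 | -0.59 | 100 | 99 | 99.8 | 96 | 99.8 | 70 |
| 0.5 | -0.50 | 100 | 92 | 98 | 83 | 97 | 50 |
| 0.7 | -0.39 | 99 | 70 | 82 | 58 | 82 | 30 |
| 0.8 | -0.32 | 92 | 52 | 65 | 38 | 64 | 20 |
| 0.9 | -0.22 | 64 | 28 | 36 | 22 | 37 | 12 |

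In the same pooled data, the treatment-by-baseline interaction was significant in 4% to 6% of trials in every scenario, as it should be. That test was run on change. With baseline in the model, the interaction coefficient is the same for the final score, since the two outcomes differ only by baseline itself.

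**Ranking instead of testing.** The plan seeks the most important measures and does not name a 5% test. With five competitors and no truncation, baseline ARI had the smallest p-value of the six in 99.6%, 97%, 89%, 76% and 54% of trials for rho 0.3, 0.5, 0.7, 0.8 and 0.9. Six equally uninformative measures would each rank first in roughly 1/6, or 17%.

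**Responder form.** Taking 0.4 SD as 0.4 SD of the change score, baseline ARI separated responders from non-responders under the null with an AUC of 0.78 (rho 0.3) down to 0.60 (rho 0.9), or 0.68 down to 0.56 when truncated. No discrimination would be 0.50.

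**The case against.** The strongest reply is that the plan is silent here, not wrong. A reader might infer that it commits to regressing change on all baseline measures without an interaction. The documents do not support that: they say only that the analysis is multivariate, and the imaging study cited for the method is described in its title as a classification approach. Treatment is also in view, since the same sentence asks what treatment influences most. This stands: the finding is that no interaction is specified, not that one is ruled out.

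A reader might also infer that a false severity finding is certain. It is not. Percentages near 100 belong to low or moderate rho with baseline ARI as the only predictor. Over 14 to 21 days rho may be higher, and truncation and competing measures lower the rate, as the table shows.

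A third tempting inference is that this artefact defeats the genotype objective. It does not, because germline genotype is not part of the change score. Genotype also has its own paragraph in 12.F, which describes those data as mainly pilot data. What carries over is only that an aim about differences in treatment response needs an arm-by-genotype term, and none is given.

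Fourth, one might argue that there are too many candidates for 104 children. The documents do not count the candidates in this analysis or say that genotype is among them. With an assumed 20 noise predictors, expected R-squared is 20/103 = 0.19, and the chance of at least one p below 0.05 is 1 - 0.95^20 = 0.64 if the tests are independent. That is an illustration, not a finding about this plan.

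Finally, the analysis is worded as a hope in an item that asks for a brief description, and no stated decision depends on it. That limits the harm. It does not turn a prognostic variable into a modifier of the drug's effect.

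**Conclusion.** The concern holds in a limited form. The plan names behavioural change as the outcome and intends to read its predictors as predictors of treatment response, without the between-arm contrast that this reading needs. Carried out as worded, the analysis is likely to present baseline severity as a predictor even if oxytocin is inert.

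The size depends on assumptions that the documents cannot settle: rho, equal variances, where the entry cut falls, the competing measures and the arms used. Across the scenarios examined, the false-signal rate ran from 12% to 100%, always above the roughly 5% of an interaction test. The direction of the problem is firm; its exact size is not. It concerns one exploratory analysis and leaves the primary ARI comparison and the 52 per arm untouched.

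**What to change.** In the last paragraph of 12.F, state that:

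- both arms are analysed, with the final score as outcome and baseline score, arm, the candidate measure and arm by measure as terms (for baseline ARI itself, arm by baseline ARI);
- any statement that a measure predicts treatment response rests on the interaction, reported with its confidence interval;
- main effects are described as prognostic only;
- the analysis is exploratory.

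Use the same arm-by-measure term for the genotype aim in item 2 and the callous-unemotional aim in the symptom-profile section. If a multivariable selection model is wanted, penalised selection with cross-validation is one option, but this correction does not require it.

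The cost is a few sentences and a little programming, with no change to data collection. The real downside is low power. For a measure that splits the sample in half, each subgroup has 26 per arm, so the SE of a subgroup effect is 7.2·√(2/26) = 2.00 and the SE of the difference between subgroups is 2.00·√2 = 2.82. An interaction as large as the planned effect gives 4.0/2.82 = 1.42, or about 29% power (normal approximation, before any gain from baseline adjustment). Fewer predictors will be claimed, and a non-significant interaction should not be read as showing an equal effect across children.
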